1.0	[REDACTED]	Original Protocol	24 July 2019
2.0	[REDACTED]	
Modified to exclude minors (i.e. under 18-year-old) from the study.
 
Clarification of entry criteria – Section 3.2.
 
Patient Release of Medical Records Form appendix removed.
	23 Sep. 2019
3.0	[REDACTED]	
Clarification of inclusion criteria 1, section 3.2: ‘... the use of a new reusable silicone hydrogel lens type and have purchased a supply of lenses.’
 
Add exclusion criteria section 3.3. non spherical lens wearers
 
Add Netherlands (country) to section 3.4 and enrollment estimation in figure 1
	03 December 2019
4.0	[REDACTED]	Language added to section 3.1 clarifying the intended study population.	24 November 2020

SYNOPSIS

[figure not shown]
Protocol Title	ACUVUE® OASYS with Transitions™ Light Intelligent Technology™ Clinical Performance Registry
Sponsor	Johnson and Johnson Vision Care, Inc. (JJVC), [name]
Clinical Phase	Post Marketing (Registry) phase 4
Trial Registration	This study will be registered on ClinicalTrials.gov by the Sponsor
Test Article(s)	Investigational Products: JJVC spherical senofilcon A with photochromic additive (ACUVUE® OASYS with Transitions™ contact lenses) Control Products: spherical non-photochromic reusable marketed silicone hydrogel contact lenses.
Wear and Replacement Schedules	Wear schedule: Daily wear Recommended replacement schedule: 2-weekly or as determined by the prescribing eyecare practitioner.
Objectives	Evaluate the performance of JJVC senofilcon A with photochromic additive (ACUVUE® OASYS with Transitions™ contact lenses) compared to non-photochromic reusable contact lenses over a period of one year in the following areas: 
 • Vision satisfaction in bright lighting • Overall quality of vision • Subjective assessment of Pulfrich Effect • Overall comfort • Reported serious or significant adverse events

Study Endpoints	
Primary endpoint:
 
 1. Vision satisfaction in bright lighting 
Secondary endpoints:
 
 1. Overall quality of vision 2. Subjective assessment of Pulfrich Effect 3. Overall comfort 4. Reported serious or significant adverse events 
Other endpoints:
 
 1. Overall satisfaction 2. Cosmetic appearance assessment 3. Lens storage compliance 4. Reasons for discontinuation 5. Other subjective assessments (indoor performance, overall opinion, average wear time, etc.)
Study Design	
This registry study is a one-year, one-visit, observational, prospective, open-label, two-arm, multi-center, multi-national, post-market study of approximately 300 patients who have recently been fitted with the ACUVUE® OASYS with Transitions™ and approximately 300 patients who have recently been fitted with spherical non- photochromic reusable marketed silicone hydrogel contact lenses (of any brand).
 
Visit 1 is conducted in-person at the eyecare practitioner (ECP) office. Assessments 2-4 are online surveys, conducted remotely.
 
 • Visit 1: Registration visit • Assessment 2: 2-week questionnaire • Assessment 3: 4-month questionnaire • Assessment 4: 12-month questionnaire 
The documentation of adverse events in the registered wearer's clinical record will reflect routine clinical practices that are outside the scope of this protocol. Medical records from any subject who reports having experienced "a problem with their eyes while wearing lenses that required you to visit an eyecare practitioner or hospital" will be obtained from the treating facility after they are reported via the 2-week, 4-month or 12-month questionnaires.
 
See the flowchart at the end of the synopsis table for the schematic of the study visits and procedures of main observations (Figure 1).

Sample Size	Approximately 600 eligible subjects will be enrolled (~300 subjects per arm) with a target of 480 to complete the study (~240 subjects per arm).
Study Duration	The study will start within 6 months of launch in a given country and will observe the clinical performance of the Test and Control lenses for approximately one year in that country.
Anticipated Study Population	
 • Patient age: minimum 18 years old, no maximum age • Patients with no known history that would contradict contact lens wear. • Neophyte patients or those refit from habitual contact lenses
Eligibility Criteria	
Potential subjects must satisfy all of the following criteria to be enrolled in the study:
 
 1. Contact lens neophytes or those who have recently (i.e. within last 2 months) begun the use of a new reusable silicone hydrogel lens type and have purchased a supply of lenses. 2. A minimum age of 18 years, with no maximum age. 3. The registrant must read and sign the Informed Consent form. 4. The registrant must appear able and willing to adhere to the instructions set forth in this clinical protocol. 
Potential subjects who meet any of the following criteria will be excluded from participating in the study:
 
 1. Current participant in another research study. 2. Employee or relative of site, or family member of Recruiting Practitioner or Johnson & Johnson. 3. Non-spherical contact lens wearers, i.e. toric or multifocal lenses.
Disallowed Medications/Interventions	Pre-study and concomitant medications are not being tracked in this Registry. Concomitant and incident therapy noted in the medical source record will be considered as part of the adjudicated diagnosis in subjects who experience events in the study.
Measurements and Procedures	
 • Physiological responses • Subjective questionnaires
Study Termination	Since all of the products associated with the study are marketed products, there are no anticipated circumstances in which the study would be prematurely terminated.

Ancillary Supplies/ Study-Specific Materials	None
Principal Investigator(s) and Study Institution(s)/Site(s)	A full list of Principal Investigators, clinical sites, and institutions is kept separately from the Study Protocol and is included in the study Trial Master File.

Figure 1: Study Flowchart

ABBREVIATIONS AND DEFINITIONS OF TERMS

ADE	Adverse Device Effect
AE	Adverse Event/Adverse Experience
CL	Contact Lens
CRA	Clinical Research Associate
CRF	Case Report Form
CRO	Contract Research Organization
DMC	Data Monitoring Committee
eCRF	Electronic Case Report Form
ECP	Eye Care Practitioner
EDC	Electronic Data Capture
ERQ	ECP Registration Questionnaire
FDA	Food and Drug Administration
GCP	Good Clinical Practice
HEV	High Energy Visible
ICF	Informed Consent Form
ICH	International Conference on Harmonization
IEC	Independent Ethics Committee
IRB	Institutional Review Board
ISO	International Organization for Standardization
JJVC	Johnson & Johnson Vision Care, Inc.
PI	Principal Investigator
PQC	Product Quality Complaint
PRO	Patient Reported Outcome
PRQ	Patient Registration Questionnaire
SAE	Serious Adverse Event/Serious Adverse Experience
SAP	Statistical Analysis Plan
SAS	Statistical Analysis System
SD	Standard Deviation
SOP	Standard Operating Procedure
UADE	Unanticipated Adverse Device Effect
USADE	Unanticipated Serious Adverse Device Effect
UK	United Kingdom
UV	Ultraviolet
VCR	Visioncare Research Ltd

1. INTRODUCTION AND BACKGROUND

In April 2018, the U.S. Food and Drug Administration (FDA) cleared the first contact lens to incorporate a photochromic additive that automatically darkens the lens in the presence of ultraviolet (UV) and high energy visible (HEV) light and lightens in its absence. The ACUVUE® OASYS with Transitions™ Light Intelligent Technology™ are soft contact lenses indicated for daily use to correct the vision and to reduce the effect of bright light. The intended users are people with non-diseased eyes who are nearsighted (myopia) or farsighted (hyperopia). They can also be used by people with certain degrees of astigmatism. The global roll-out of the lens began in the spring of 2019, with countries being added over forthcoming years.

The goal of this registry study is to provide real world data on the effectiveness of ACUVUE® OASYS with Transitions™ in the general population of spherical contact lens wearers and under general clinical practice. Vision satisfaction in bright lighting and overall quality of vision will be assessed using a longitudinal survey questionnaire over a period of one year. Pulfrich effect and reported serious and significant ocular adverse events will also be evaluated. This a non-randomized study and the sponsor, Johnson and Johnson Vision Care, Inc. (JJVC), has no control of the treatment assignment and minimal input on the study targeted population.

The sponsor has contracted with Visioncare Research (VCR) to monitor the study.

This Clinical Investigation Plan is to be used in conjunction with JJVC standard operating procedures (SOPs) (except for as outlined in this plan) as a project-specific working plan by VCR and designees during the conduct of the study. The following plan provides the minimum acceptable criteria for this study. This plan does not replace an understanding or adherence to the requirements contained in the study protocol, applicable regulations and ICH/GCP guidelines.

1.1. Name and Descriptions of Investigational Products

All products are approved and marketed within the countries participating in this Registry study. ACUVUE® OASYS with Transitions™ will serve as the Test lens. Other reusable spherical silicone hydrogel lenses will serve as the Control lenses. Further details about the Test lenses are found in Section 6 of this protocol.

1.2. Intended Use of Investigational Products

The intended use of the Test product is for correcting ametropia and the attenuation of bright light. During the study, the Test article will be worn bilaterally in a daily wear, reusable, 2-weekly modality, or as determined by the prescribing eyecare practitioner (ECP).

1.3. Summary of Findings from Nonclinical Studies

Not Applicable – Marketed product only.

1.4. Summary of Known Risks and Benefits to Human Subjects

The risks of wearing soft contact lenses are well known and are described in the relevant Package Insert.

1.5. Relevant Literature References and Prior Clinical Data Relevant to Proposed Clinical Study

Refer to relevant Package Insert.

2. STUDY OBJECTIVES, ENDPOINTS AND HYPOTHESES

2.1. Objectives

The objective of this study is to evaluate the performance of JJVC senofilcon A with photochromic additive (ACUVUE® OASYS with Transitions™ contact lenses) compared to non-photochromic reusable contact lenses over a period of one year in the following areas:

- Vision satisfaction in bright lighting
- Overall quality of vision
- Subjective assessment of Pulfrich Effect
- Overall comfort
- Reported serious or significant adverse events

2.2. Endpoints

All of the primary and secondary endpoints will be assessed using the follow-up questionnaire administered at 2-weeks, 4-months and 12-months after the enrollment visit (Visit 1).

Primary endpoints

Vision Satisfaction in Bright Lighting

Subjects will be asked to evaluate their vision satisfaction in bright lighting by rating their level of agreement with the statement “I was satisfied with the quality of my vision in bright lighting with these contact lenses” using a 5-point agreement Likert scale (1: Strongly Disagree, 2: Disagree, 3: Neither Agree nor Disagree, 4: Agree and 5: Strongly Agree).

Secondary endpoints

Overall quality of vision

This will be assessed subjectively using the item “I am satisfied with the overall quality of my vision with these contact lenses”. The item uses a 5-point agreement scale (1: Strongly Disagree to 5: Strongly Agree)

Pulfrich Effect

This will be assessed subjectively using the item “While wearing these lenses, my depth perception of moving objects has NOT been impacted”. Subjects who disagree or strongly disagree with the statement will be considered to have experienced the Pulfrich effect.

Overall comfort

This will be assessed using the item “How would you rate the overall comfort of these contact lenses?”. The item uses the 5-point satisfaction scale, 1: Excellent, 2: Very Good, 3: Good, 4: Fair and 5: Poor.

Reported serious and significant ocular adverse events:

Incidence rate serious and significant ocular adverse events during the study period will be calculated (in 100 patient-year) using all available data from the entire study.

Other endpoint(s):

1. Overall satisfaction
2. Cosmetic appearance assessment
3. Lens storage compliance
4. Reasons for discontinuations
5. All reported ocular and non-ocular adverse events
6. Other subjective assessments (indoor performance, overall opinion, average wear time, etc.)

2.3. Hypotheses

Primary Hypotheses

Subjects wearing JJVC senofilcon A contact lenses with photochromic additive (ACUVUE® OASYS with Transitions™ contact lenses) will have superior vision satisfaction in bright lighting compared to subjects wearing non-photochromic reusable silicone hydrogel contact lenses over a period of one year.

Secondary Hypotheses

1. Subjects wearing JJVC senofilcon A contact lenses with photochromic additive (ACUVUE® OASYS with Transitions™ contact lenses) will have superior vision satisfaction compared to subjects wearing non-photochromic reusable silicone hydrogel contact lenses at 12-month evaluation. This hypothesis will also be tested at 2-week and 4-month evaluation periods.
2. Subjects wearing JJVC senofilcon A contact lenses with photochromic additive (ACUVUE® OASYS with Transitions™ contact lenses) will have superior overall quality of vision compared to subjects wearing non-photochromic reusable silicone hydrogel contact lenses over a period of one year. This hypothesis will also be tested at each evaluation period.
3. Subjects wearing JJVC senofilcon A contact lenses with photochromic additive (ACUVUE® OASYS with Transitions™ contact lenses) will have superior overall comfort compared to subjects wearing non-photochromic reusable silicone hydrogel contact lenses over a period of one year. This hypothesis will also be tested at each evaluation period.

No hypotheses are formulated about Pulfrich effect or, serious and significant ocular adverse events (AEs). The following will be calculated by arm:

1. Proportion of subjects who experienced the Pulfrich effect at each evaluation period.
2. Incidence rate of serious and significant ocular AEs (in patient-year)

3. Proportion of subjects with at least one reported serious or significant ocular AE at each evaluation period.
4. Proportion of eyes with at least one reported serious or significant ocular AE at each evaluation period.
5. Proportion of all reported serious and significant ocular AEs at each evaluation period.

3. TARGETED STUDY POPULATION

3.1. General Characteristics

Subjects may be of any race, nationality, and ethnicity that meet the following inclusion and exclusion criteria. Subjects will not be fitted with contact lenses specifically for the purposes of this study. Instead, patients recently fitted or refitted with contact lenses will be invited to take part in this observational study.

3.2. Inclusion Criteria

Potential subjects must satisfy all of the following criteria to be enrolled in the study:

Inclusion Criteria after Screening:

1. Contact lens neophytes or those who have recently (i.e. within last 2 months) begun the use of a new reusable silicone hydrogel lens type and have purchased a supply of lenses.
2. A minimum age of 18 years, with no maximum age.
3. The registrant must read and sign the Informed Consent form.
4. The registrant must appear able and willing to adhere to the instructions set forth in this clinical protocol.

For clarification, non-neophyte subjects may include previous wearers of any type of soft contact lens (e.g. daily disposable), however, the new lens type must be a reusable silicone hydrogel. Also, non-neophyte subjects may have previously worn soft contact lenses at any point in time; in other words, it is not necessary for recently refitted subjects to have transitioned from their old to new lenses without a break in wear.

3.3. Exclusion Criteria

Potential subjects who meet any of the following criteria will be excluded from participating in the study:

Exclusion Criteria after Screening:

1. Current participant in another research study.
2. Employee or relative of site, or family member of Recruiting Practitioner or Johnson & Johnson.
3. Non-spherical contact lens wearers, i.e. toric or multifocal lenses.

3.4. Enrollment Strategy

Study subjects will be recruited from the clinical site's subject database and/or utilizing Independent Ethics Committee (IEC) or Institutional Review Board (IRB) approved materials.

Site recruitment based on actively prescribing a new device is a method that has been used in two prior post-market surveillance studies for FDA.^{5,6} Proposed regions include but are not limited to areas within the United Kingdom (UK), Spain, Netherlands and Germany. Regions will be replaced or supplemented if there is inadequate response to invitations to participate.

The Principal Investigator and CRO will recruit sub-investigators, referred to as ‘Recruiting Practitioners’ throughout this document at clinical sites. Clinical sites in the selected regions that are actively prescribing the ACUVUE® OASYS with Transitions™ lenses will be invited to participate as Recruiting Practitioners. Recruiting Practitioners will be allowed a maximum of 50 registered wearers per site, so that no one site will contribute more than 25% of the sample population in a given country. The study anticipates unequal enrollment across the sites, as their rate of prescribing ACUVUE® OASYS with Transitions™ will vary considerably. Unequal enrollment should reflect the population exposures to the Test lens and follows the tenets of surveillance. A convenience, rather than random, sample is necessary for the study because ACUVUE® OASYS with Transitions™ contact lenses have not yet been widely launched and are only available to some eye care practitioners. Thus, active prescribers of ACUVUE® OASYS with Transitions™ lenses will be invited to participate within each region in order to provide a large enough sample size for the study.

Within sites, wearers of ACUVUE® OASYS with Transitions™ lenses will be invited to participate without regard to any demographic or other ocular features. Wearers will be registered after they have recently (i.e. within last 2 months) received a prescription for and a supply of ACUVUE® OASYS with Transitions™ lenses.

The study design also allows an unconstrained relative proportion of ACUVUE® OASYS with Transitions™ lenses within a site in order to reflect the exposure profile present in that site. When the study has enrolled 300 Test lens subjects, enrollment will be actively curtailed but leaving the enrollment open to the other lens type until complete (or vice versa).

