5. TEST ARTICLE ALLOCATION AND MASKING

5.1. Test Article Allocation

This is a non-randomized observational study. Subjects receiving a new lens brand as part of the routine practice at the investigational site will be asked to participate:

- Subjects receiving an ACUVUE® OASYS with Transitions™ contact lens on both eyes will comprise the Test group.
- Subjects receiving any other spherical silicone hydrogel lens to be worn as daily wear and frequent replacement (2-weekly or monthly) will comprise the Control group.
- The Test/Control allocation per site is approximately 1:1. Sites should not recruit a larger number of control subjects than test subjects.

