5.2. Masking

This is an open label registry study. The identity of the lenses is known to all. Given this, there are no procedures for maintaining and breaking the masking.

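### Neither arm has an order-of-invitation rule, so where the per-site limit on Controls binds, an unmasked practitioner decides which Control wearers to register

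*Combined protocol and SAP*

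**What the plan says.** On Test wearers, Section 3.4 states: "Within sites, wearers of ACUVUE® OASYS with Transitions™ lenses will be invited to participate without regard to any demographic or other ocular features". It then ties registration to a Test prescription and supply within the last 2 months. It has no parallel sentence for Controls.

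On both arms together, Section 5.1 states: "Subjects receiving a new lens brand as part of the routine practice at the investigational site will be asked to participate". It defines the Control group as "Subjects receiving any other spherical silicone hydrogel lens to be worn as daily wear" with 2-weekly or monthly replacement, and adds: "The Test/Control allocation per site is approximately 1:1. Sites should not recruit a larger number of control subjects than test subjects". Section 4.3 likewise expects similar numbers of Test and Control subjects at each site.

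Section 3.4 points the other way. It allows the proportion of Test lenses within a site to be unconstrained so that it reflects that site's prescribing. When one arm reaches 300, enrolment stays open for the other.

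Other relevant statements:
- Source of subjects (Section 3.4): "Study subjects will be recruited from the clinical site's subject database", and/or through approved recruitment materials.
- Masking (Section 5.2): "The identity of the lenses is known to all".
- Approach to the wearer (Section 7.2, step 1.1): made by the Recruiting Practitioner or staff.
- Prior wear (Section 3.2): refitted wearers may have started the new lens up to 2 months earlier.
- Adjustment (Section 14.5): baseline values, country, age, gender and race where appropriate, site as a random effect, and a propensity score.

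**The concern.** The primary endpoint is the wearer's own rating of satisfaction in bright light. If a site has more eligible Controls than it may register, some are left out, and the plan does not say which. The person deciding knows the lens and may have seen the patient after several weeks of wear. If the decision is related to how satisfied the wearer is or is expected to be, it acts on the primary outcome itself.

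The planned adjustment balances recorded characteristics. It corrects this kind of selection only as far as the baseline values capture it. The plan provides no log of eligible wearers who were not invited or who declined, so the selection could not be examined afterwards.

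A false superiority finding is at stake if less satisfied Controls are registered, and lost power if more satisfied ones are.

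**Working it through.** **Inputs from the plan (Section 14.2 and Table 3).** Control 77.1%, Test 86.6%, three observations per subject, correlation ρ of 0.3 to 0.7, two-sided 0.05, at least 80% power, 240 completing and 300 enrolled per arm.

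**Input assumed.** The size of any selection shift. The documents give none.

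**Step 1. The plan's own figures.** The formula in Section 14.2 gives 194.0 per arm for 0.77 against 0.86 at ρ = 0.5 (printed 194), and 234.5 for 0.70 against 0.80 at ρ = 0.7 (printed 234). Thirteen of the 15 cells of Table 4 reproduce to within rounding. The two that do not, both in the last row, do not bear on this point. Power at 240 per arm runs from 80.9% to 97.9% across the scenarios, so the stated 80% minimum holds. Enrolment is 240/(1 − 0.20) = 300.

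**Step 2. Odds ratio implied by Table 3.** (0.866/0.134) / (0.771/0.229) = 6.463/3.367 = 1.92.

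**Step 3. Odds ratio from selection alone.** Suppose there is no lens effect, 77.1% are satisfied in both populations, and the registered Controls are s points less satisfied than all eligible Controls. Then OR = odds(0.771)/odds(0.771 − s).

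| Assumed shift s | Registered Controls satisfied | Apparent OR |
|---|---|---|
| 2 points | 75.1% | 3.367/3.016 = 1.12 |
| 3 points | 74.1% | 3.367/2.861 = 1.18 |
| 5 points | 72.1% | 3.367/2.584 = 1.30 |

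The apparent OR equals the factor k by which a dissatisfied Control is more likely to be registered than a satisfied one. The registered odds are p/[(1 − p)k], so dividing p/(1 − p) by them leaves k. A 5-point shift therefore needs dissatisfied Controls to be about 1.3 times as likely to be registered.

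**Step 4. Chance of a false superiority finding.** With 240 per arm, the effective number per arm is 240 × 3/(1 + 2ρ), which is 450, 360 or 300 at ρ = 0.3, 0.5 or 0.7. The chance is Φ[(s − 1.96·se0)/se1], with se0 the pooled and se1 the unpooled standard error, unadjusted for covariates. Going from ρ = 0.7 to ρ = 0.3:

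- 2 points: 8% to 10%
- 3 points: 14% to 18%
- 5 points: 29% to 41%

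The nominal chance in that direction is 2.5%.

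**Step 5. The other direction.** If satisfied Controls are 1.25 times as likely to be registered, Control satisfaction rises from 77% to 80.7%. Power against a Test rate of 86% then falls from 81–94% to 41–57%.

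**The case against.** Several stronger readings are tempting, and the documents do not support them.

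- *The plan lets practitioners pick their Controls.* A reader might infer this, but no section grants it. Section 5.1 says that people receiving a new lens brand will be asked. The plan is silent on order, which is different from permitting a choice.
- *Only the Control arm is exposed.* The Test sentence bars selection on demographic or ocular features. It does not mention satisfaction and is not a consecutive rule. Test wearers have the same 2-month window and the same unmasked practitioner, and similar selection in both arms would partly cancel.
- *The reason for convenience sampling covers Test only.* Section 3.4 says "A convenience, rather than random, sample is necessary for the study because ACUVUE® OASYS with Transitions™ contact lenses have not yet been widely launched", but uses this to explain why active prescribers are chosen as sites. Controls come from the same sites.
- *Sites will have a surplus of Controls.* This is an inference. Eligible Controls must have bought a new reusable spherical silicone hydrogel lens. Torics, multifocals and people newly fitted with daily disposables are out. No counts are given.
- *Adjustment cannot help.* Baseline values enter the model and a Patient Registration Questionnaire is completed at Visit 1. Its content is not visible here and further detail is deferred to a separate SAP, so some correction is possible.

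It is also fair to say that the plan discloses convenience sampling, open-label use and possible baseline differences. Practitioners are not said to collect satisfaction before registration, and recruitment through approved materials need not begin with a practitioner's choice.

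What remains is that no order of invitation exists for either arm, the sections disagree on whether the within-site ratio is limited, and nothing is recorded that would show who was left out. Calling the study observational does not answer this, because it tests a superiority hypothesis and an invitation order would not touch lens assignment.

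**Conclusion.** The gap is in the text and is certain; the size of any bias is not. Both arms lack an order of invitation. Sections 4.3 and 5.1 conflict with Section 3.4 on the within-site ratio, and that conflict decides how often some Controls must be left out. Where the limit binds and Controls are in surplus, registration of Controls rests on site discretion with respect to a subjective primary outcome.

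Shifts of 2 to 5 points would move the odds ratio from 1 to between 1.12 and 1.30, well short of 1.92 but enough to raise the false-superiority chance several-fold. These figures assume no lens effect, 77.1% in both populations, selection among Controls only, and no correction by covariates. A reader might infer that the bias favours the Test lens. The documents give no direction, and favouring satisfied Controls would work against it. The change should be made, with medium confidence in how much it matters.

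**What to change.** In Sections 3.4 and 5.1, state the following:

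- Sites invite eligible wearers in both arms consecutively by lens supply date, without regard to demographic or ocular features or to known or expected satisfaction.
- When the Control limit is reached at a site, Control invitations pause, then resume with the next consecutive eligible patient.
- After the Test arm closes, Control invitations continue consecutively until that arm is complete. Tying each Control invitation to a Test registration would stall Control enrolment at this stage, so it should be avoided.

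Reconcile the unconstrained proportion in Section 3.4 with the roughly 1:1 expectation in Sections 4.3 and 5.1. Keep a one-line invitation log per site (lens, supply date, accepted or declined) and report acceptance by arm.

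The cost is protocol wording, a small logging burden for existing site staff and possibly slower Control registration. The targets of 240 completing and 300 enrolled per arm stay as they are.
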